7.3.2. Outcome definitions

The 2 primary outcomes that will be evaluated are:

- 1. New-onset GBS, and
- 2. New-onset ADEM.

The 1 secondary outcome that will be evaluated is: New-onset AF.

7.3.2.1. Medical record review of primary and secondary outcomes

At each annual monitoring query, for the evaluation of primary outcomes (i.e., GBS and ADEM), screening for potential events in the administrative claims data of the RPs will be done using the case-finding algorithms described in Table 4. Once each annual monitoring query is complete, given the rarity of GBS and ADEM, we will immediately seek to obtain the medical records of all patients identified as having possible events

based on our algorithms, abstract the data necessary to confirm these diagnoses from the medical records obtained, and implement a formal adjudication process with a team of expert clinicians, preferably neurologists, to confirm these events. Only confirmed cases will be included in the final primary analyses. For those outcomes, timing of symptom onset will be discerned from medical record review and timing of the event will be classified based on expert clinician adjudication (i.e., the date of diagnosis from the claims data will not be used due to concerns with misclassification).

Since AF is a more frequent health outcome in the population of interest compared to GBS and ADEM, a conventional approach will be followed to confirm the validity of the algorithms for each of these outcomes during the initial annual monitoring queries (we anticipate that the sample sizes for each AF validation can be accrued within the first or second annual monitoring periods given the prevalence of AF in the age group of the study population, but will need to assess initial monitoring query results) [Weinstein, 2023]. For the AF outcome, we *a priori* seek to identify an algorithm that has a positive predictive value (PPV) of \geq 80% to provide confidence that identified outcomes are true events. We estimate that 63 patients' charts (complete and adjudicated) would allow determination of the PPV of each case-finding algorithm with a maximum 95% CI of \pm 10%, assuming a PPV of 80% (Table 3).

The number of adjudicated charts needed for the AF validation will be determined based on the number of AF cases identified in the monitoring query(s). We expect to conduct the validation within 1-2 RPs, including the one RP with the most AF events identified during the initial monitoring queries.

Note that for analyses that include claims-based outcomes of interest in the inpatient setting, admission dates will be used, not discharge dates.

Number of AF cases identified	1 000	5 000	10 000	20 000	100 000		
Actual PPV	Number	Number of adjudicated charts needed					
60%	86	92	93	93	94		
65%	82	87	88	89	89		
70%	76	81	82	82	82		
75%	69	72	73	73	73		
80%	59	62	63	63	63		
85%	48	50	50	50	50		
90%	35	36	36	36	36		

Table 3Number of charts needed to obtain a 95% two-sided Cl ±10% for
new-onset AF validation*

Abbreviations: AF: atrial fibrillation CI: confidence interval; PPV: positive predictive value.

*The needed sample size for a 2-sided 95% CI for a binomial proportion with a 10% margin of error was calculated using a range of possible AF cases. These calculations were done in Excel.

To account for the fact that approximately 30%, or more, of hospital medical records might not be available to review, we will oversample from a random sample of the total AF cases identified according to the case-finding algorithm to ensure we obtain the target number of charts needed. Once the initial annual monitoring query, which will include new-onset AF, is complete, medical records of patients in the sample will be requested immediately. Once charts have returned, the data necessary to confirm these diagnoses from the medical records will be abstracted, implement a formal adjudication using a team of expert clinicians, preferably cardiologists, to confirm these events, and determine the PPV of the algorithm for new-onset AF.

Medical records will be obtained from participating RPs in a manner compliant with the Health Insurance Portability and Accountability Act (HIPAA) and local privacy regulations. Hospital and outpatient charts will be obtained directly through requests from RPs using identifiers obtained from administrative claims data. Designated protected health information users at each RP will link the protected health information with masked patient identification numbers, dates of birth, and provider information for the patients identified for medical record abstraction. As noted above, charts are not expected to be 100% obtainable from participating RPs and that ~30% of charts sought can be unobtainable based on prior experience. Section 7.7.2 includes description of how potential events with unobtainable charts will be handled in the analyses. Bias will not be expected based on whether charts were obtainable or unobtainable (reasons for charts being unobtainable include providers being non-responsive or providers incorrectly assuming patient authorization is required). Table 4 below summarizes the proposed diagnosis code-based case-finding algorithms and key elements of the validation of each outcome.

Table 4 Case-finding algorithms and risk and control windows for outcomes of interest

Outcome	Diagnosis code(s) to identify event	Event identification care setting and details	Risk window	Control window, Extra days	Look-back period for outcome-free window	Diagnosis code(s), care setting for outcome-free period	Published algorithm data	Chart review considerations
New- onset GBS	G61.0 ^a	CC1	Primary: 1-42 days [Sejvar, 2011; Goud, 2021; Britton, 2024 Lloyd 2024]	Control window: 43-84 days, Extra days: 7	-365 through - 1 (day 0 is day of event), as previously conducted [Polakowski, 2013]	G61.0 or G65.0, inpatient setting (any position)	 PPV from studies using Medicare data: (1) 78.57% (95% CI, 63.37%- 93.77%) [Goud, 2021] (2) 71.21% (95% CI: 63.49%-78.94%) 	Will seek charts on all events. Final analysis will include chart- confirmed events only.
			Sensitivity: (a) 1-21 days and (b) 8-28 days				[Arya, 2019]; (3) 68.0% (95% CI: 56.8%- 77.5%) [Lloyd, 2024]	

220149 (EPI-RSV-041 OA VS US DB) Protocol Amendment 2 Final

Outcome	Diagnosis code(s) to identify event	Event identification care setting and details	Risk window	Control window, Extra days	Look-back period for outcome-free window	Diagnosis code(s), care setting for outcome-free period	Published algorithm data	Chart review considerations
New- onset ADEM	G04.00, G04.01, G04.02 ^b	CCI	Primary: 1-42 days Sensitivity: a) 1-21 days and (b) 8-28 days	Control window: 43-84 days, Extra days: 7	-365 through - 1 (day 0 is the day of the event)	G04.00, G04.01, or G04.02, inpatient setting (any position)	ICD-10-CM based algorithm not available	Will seek charts on all events. Final analysis will include chart- confirmed events only.

220149 (EPI-RSV-041 OA VS US DB) Protocol Amendment 2 Final

Outcome	Diagnosis code(s) to identify event	Event identification care setting and details	Risk window	Control window, Extra days	Look-back period for outcome-free window	Diagnosis code(s), care setting for outcome-free period	Published algorithm data	Chart review considerations
New- onset AF	See Table 7	CCI	Primary: 1-8 days	Primary: 9-16 days	-365 through day -1 (day 0 is day of the	Any indicated AF diagnosis ir Table 7 in any care setting	PPV for ICD-10-CM (I48) based algorithms ranged from 67.5%-	Will aim to review charts from ~63 presumed cases from selected RPs to determine RBV d
			Sensitivity (a): 1-28 days	Sensitivity (a): 29-56 days	event)		75.7% [Chamberlain, 2022]	to determine PPV
			Sensitivity (b): 1-3 days	Sensitivity (b): s4-8 days				
				Extra days: 0				

Abbreviations: AF: atrial fibrillation; ADEM: acute disseminated encephalomyelitis; ED: emergency department; GBS: Guillain-Barré syndrome; ICD-10-CM: International Classification of Diseases, tenth revision, clinical modification; PPV: positive predictive value.

a. GBS ICD-10-CM codes and descriptions:

G61.0: Guillain-Barré syndrome

G65.0: sequelae of Guillain-Barré syndrome

b. ADEM ICD-10-CM codes and descriptions:

G04.00: Acute disseminated encephalitis and encephalomyelitis, unspecified G04.01: post-infectious acute disseminated encephalitis and encephalomyelitis, G04.02: Postimmunization acute disseminated encephalitis, myelitis, and encephalomyelitis.

Note that for AF, if the first qualifying diagnosis code occurs on Day 16, then the last possible second code would be on Day 106.

d. The final number of complete, adjudicated charts needed for AF will be based on the number of AF cases identified, as summarized in Table 3.

C.

7.3.2.2. Ascertainment and confirmation of GBS events

Screening for GBS:

Within each RP's database, patients will be identified as having possible GBS within 91 days after *Arexvy* vaccination (primary analysis risk window days 1-42, control window days 43-84, and 7 extra days) if they had either:

. The claims-based

case date for cases will be based on the earliest diagnosis of interest. New-onset GBS will be identified by requiring that there is no evidence of GBS in the 365 days prior to the first diagnosis code of interest: no occurrence of G61.0 (GBS) or G65.0 (Sequelae of GBS) hospital discharge diagnosis (any position) in days -365 through day -1 (day 0 is the day of the event).

The primary risk window will be 42 days as several prior vaccine safety studies of postvaccination GBS have used a 42-days window [Arya, 2019; Goud, 2021; Britton, 2024; Lloyd, 2024], and that precedent will be followed. Sensitivity analyses using risk windows of (a) days 1-21 and (b) days 8-28 will be included based on the timing of postmarketing reports of GBS, other studies of post-vaccination GBS [Klein, 2021], and the timing of the 1 reported GBS case in the *Arexvy* clinical trials [Melgar, 2023].

The control window will be days 43-84 following vaccination for both primary and sensitivity analyses' risk windows. Continuous enrolment will be required through the end of the respective control interval plus 7 extra days to ensure that diagnosis codes that are recorded after symptom onset (and potentially after the risk and comparison windows) are captured. The final analyses will include individuals with an event of interest and who die during the 91-days follow-up period.

Validation of GBS events:

Materials for medical record review (including the abstraction and adjudication forms with case classifications and standard operating procedures [SOPs]) will be developed prior to having results from the first monitoring query. Given the expected rarity of GBS events after *Arexvy* vaccination, we will attempt to obtain medical records for all vaccinees who meet the above algorithm for GBS and multiple attempts will be made for each medical record as necessary. Events of interest whose charts are unobtainable will not be included in the inferential analyses. We will review summary information from their claims data, request the hospital records of these individuals, abstract relevant data to permit confirmation of GBS, and conduct a formal adjudication to arbitrate the presence and date of onset of symptoms of the event. Inpatient medical records will be obtained from each of the RPs in a manner compliant with the HIPAA and privacy regulations. Hospital charts will be obtained directly through requests from RPs using identifiers obtained from administrative claims data. Designated protected health information with masked

patient identification numbers, dates of birth, and provider information for the patients identified for medical chart abstraction.

A trained abstractor will extract specific information from the hospital records onto a structured data abstraction form. The form will collect information from admission notes, discharge summaries, laboratory results, radiographic reports, neurologist consultation notes, inpatient progress notes, and relevant medications administered. Forms will be independently reviewed by 2 clinicians, preferably neurologists, who will use the Brighton Collaboration's case definition for GBS (Table 5) to adjudicate whether a case is confirmed, possible, or not an event [Sejvar, 2011]. Disagreements in GBS case classification will be arbitrated by a third clinician, preferably a neurologist. GBS cases identified as Brighton Level 1, 2, or 3 will be considered medical record-confirmed cases. GBS cases identified as Level 4 (lowest level of certainty) will be considered possible GBS cases. Level 5 events will not be considered cases. Abstractors and adjudicators will be blinded to vaccination date – i.e., they will not know whether the event occurred in the risk or control window.

Table 5	Brighton Collaboration GBS case classification levels of diagnostic
	certainty and criteria

Brighton level of diagnostic	Criteria
certainty	
Level 1 (Highest Level of Certainty)	Bilateral AND flaccid weakness of the limbs. Decreased or absent deep tendon reflexes in weak limbs. Monophasic illness pattern AND interval between onset and nadir of weakness between 12h and 28 days AND subsequent clinical plateau. The eventual outcome is either stabilization at nadir OR subsequent improvement OR death. Electrophysiologic findings consistent with GBS. Cytoalbuminologic dissociation (i.e., elevation of CSF protein level above laboratory normal value AND CSF total white cell count <50 cells/µL). Absence of identified alternative diagnosis for weakness.
Level 2	Bilateral AND flaccid weakness of the limbs. Decreased or absent deep tendon reflexes in weak limbs. Monophasic illness pattern AND interval between onset and nadir of weakness between 12h and 28 days AND subsequent clinical plateau. CSF total white cell count <50 cells/µL (with or without CSF protein elevation above laboratory normal value) OR If CSF not collected or results not available, electrophysiologic studies consistent with GBS. Absence of identified alternative diagnosis for weakness.
Level 3	Bilateral AND flaccid weakness of the limbs. Decreased or absent deep tendon reflexes in weak limbs. Monophasic illness pattern AND interval between onset and nadir of weakness between 12h and 28 days AND subsequent clinical plateau. Absence of identified alternative diagnosis for weakness.
Level 4 (Lowest Level of Certainty)	A case will be classified as having "insufficient evidence" if a physician's diagnosis of GBS is made, but evidence is insufficient to classify the patient at any higher level of diagnostic certainty (i.e., the abstraction data for that case does not contradict any of the Level 3 criteria but is missing information for at least one of the Level 3 criteria). Absence of identified alternative diagnosis for weakness.
220149 (EPI-RSV-041 OA VS US DB) Protocol Amendment 2 Final

Brighton level of diagnostic	Criteria
certainty	
Level 5 (Not a case)	If a case does not meet the criteria necessary for classification as Brighton Level 1, 2, or 3, is not diagnosed as GBS by a physician, or has a definitive alternate diagnosis documented in the chart, the patient will be classified as "not GBS."

Abbreviations: CSF: cerebrospinal fluid; GBS: Guillain-Barré syndrome; h: hours.

The adjudicator will record the date, or estimated date, that symptoms first appeared per information in the chart. This will be the date used in the final analyses, described in Section 7.7. The onset date is crucial to determining whether the outcome occurred during the risk or control window.

7.3.2.3. Ascertainment and confirmation of ADEM events

Ascertainment and confirmation of ADEM events will follow the same approach as GBS.

Screening for ADEM:

Within each RP's database, patients will be identified as having possible ADEM within 91 days after *Arexvy* vaccination (primary analysis risk window days 1-42, control window days 43-84, and 7 extra days) if they had either:

. The claims-based case date will be based on the earliest diagnosis of interest. New-onset ADEM will be identified by requiring that there not be evidence of ADEM in the 365 days prior to the first diagnosis code of interest: no occurrence of G04.00, G04.01, or G04.02 hospital discharge diagnosis (any position) in days -365 through day -1 (day 0 is the day of the event). We are identifying potential cases using the G04.01 diagnosis code, post-infectious acute disseminated encephalitis and encephalomyelitis, because only chart-confirmed ADEM will be included in the final analysis. The diagnosis code for post-infectious acute disseminated encephalitis will be included to ensure we identify all potential outcomes post-vaccination; a patient code be miscoded as have a post-infectious event and we are prioritizing sensitivity of the algorithm over specificity given that charts on all events identified will be obtained.

The sensitivity analyses will use risk windows of (a) 1-21 days and (b) days 8-28, both with a control window of days 43-84, to align with the GBS approach, the timing of the 2 ADEM cases reported in the clinical trial, and other studies of postvaccination ADEM [Rongxia, 2016; Klein, 2021]. Symptom onset for the 2 ADEM events reported during *Arexvy* clinical trials – which were ultimately revised to other diagnoses – was on days 7 and 22 [Melgar, 2023].

The control window will be days 43-84 following vaccination. Continuous enrolment will be required through the end of the respective control interval plus 7 extra days to ensure that diagnosis codes that are recorded after symptom onset (and potentially after the risk and comparison windows) are captured. The final analyses will include individuals who have ADEM and die during the 91-days follow-up window.

Validation of ADEM Events:

Materials for medical record review (including the abstraction and adjudication forms with case classifications and SOPs), will be developed prior to having results from the first monitoring query. Given the expected rarity of ADEM events after Arexvy vaccination, we will attempt to obtain medical records for all vaccinees who meet the above algorithm for ADEM, and multiple attempts will be made for each medical record as necessary. Events of interest whose charts are unobtainable will not be included in the inferential analyses. We will review summary information from their claims data, request the hospital records of these individuals, abstract relevant data to permit confirmation of ADEM, and conduct a formal adjudication to arbitrate the presence and date of onset of symptoms of the event. Inpatient medical records will be obtained from each of the RPs in a manner compliant with HIPAA and privacy regulations. Hospital charts will be obtained directly through requests from RPs using identifiers obtained from administrative claims data. Designated protected health information users at each RP will link the protected health information with masked patient identification numbers, dates of birth, and provider information for the patients identified for medical chart abstraction.

A trained abstractor will extract specific information from the hospital records onto a structured data abstraction form. The form will collect information from admission notes, discharge summaries, laboratory results, radiographic reports, neurologist consultation notes, inpatient progress notes, and relevant medications administered. Forms will be independently reviewed by 2 clinicians, preferably neurologists, to adjudicate whether a case is confirmed, possible, or not an event [Sejvar, 2007]. Disagreements in ADEM case classification will be arbitrated by a third clinician, preferably a neurologist. ADEM cases identified as Brighton Level 1, 2, or 3 will be considered medical record-confirmed cases. ADEM cases identified as Level 4 (lowest level of certainty) will be considered possible ADEM cases. Level 5 events will not be considered cases (Table 6). Abstractors and adjudicators will be blinded to vaccination date – i.e., they will not know whether the event occurred in the risk or control window.

Table 6 Brighton Collaboration ADEM case classification levels of diagnostic certainty and criteria

Brighton level of diagnostic certainty	Criteria
Level 1 (Highest Level of Certainty)	Demonstration of diffuse or multifocal areas of demyelination by histopathology. OR
	2a. Focal or multifocal findings referable to the central nervous system, including one or more of the following:
	Encephalopathy
	Focal cortical signs (including but not limited to: aphasia, alexia, agraphia, cortical blindness)
	Cranial nerve abnormality/abnormalities

Brighton level of diagnostic certainty	Criteria				
	Visual field defect/defects				
	Presence of primitive reflexes (Babinski's sign, glabellar reflex,				
	snout/sucking reflex)				
	Sensory abnormalities (either positive or negative sensory level)				
	Altered deep tendon reflexes (hypo- or hyperreflexia, asymmetry of reflexes)				
	Cerebellar dysfunction, including ataxia, dysmetria, cerebellar nystagmus				
	AND				
	2b. Magnetic resonance imaging findings displaying diffuse or multifocal white matter lesions on T2-weighted, diffusion-weighted (DWI), or fluid-attenuated inversion recovery (FLAIR) sequences (± gadolinium enhancement on T1 sequences).				
	AND				
	2c. Monophasic pattern to illness (i.e., absence of relapse within a minimum of 3 months of symptomatic nadir.				
Level 2	1a. Focal or multifocal findings referable to the central nervous system, including one or more of the following:				
	Encephalopathy				
	Focal cortical signs (including but not limited to: aphasia, alexia, agraphia, cortical blindness)				
	Cranial nerve abnormality/abnormalities				
	Visual field defect/defects				
	Presence of primitive reflexes (Babinski's sign, glabellar reflex, snout/sucking reflex)				
	Motor weakness (either diffuse or focal; more often focal)				
	Sensory abnormalities (either positive or negative sensory level)				
	Altered deep tendon reflexes (hypo- or hyperreflexia, asymmetry of reflexes)				
	Cerebellar dysfunction, including ataxia, dysmetria, cerebellar nystagmus				
	AND				
	1b. Magnetic resonance imaging findings displaying diffuse or multifocal white matter lesions on T2-weighted, diffusion-weighted (DWI), or fluid-attenuated inversion recovery (FLAIR) sequences (± gadolinium enhancement on T1 sequences).				
	AND				
	1c. Insufficient follow-up time achieved to document absence of relapse within a minimum period of 3 months following symptomatic nadir.				

220149 (EPI-RSV-041 OA VS US DB) Protocol Amendment 2 Final

Brighton level of diagnostic certainty	Criteria		
Level 3	Focal or multifocal findings referable to the central nervous system, including one or more of the following:		
	Encephalopathy		
	Focal cortical signs (including but not limited to: aphasia, alexia, agraphia, cortical blindness)		
	Cranial nerve abnormality/abnormalities		
	Visual field defect/defects		
	Presence of primitive reflexes (Babinski's sign, glabellar reflex,		
	snout/sucking reflex)		
	Motor weakness (either diffuse or focal; more often focal)		
	Sensory abnormalities (either positive or negative sensory level)		
	Altered deep tendon reflexes (hypo- or hyperreflexia, asymmetry of reflexes)		
	Cerebellar dysfunction, including ataxia, dysmetria, cerebellar nystagmus		
Level 4 (Lowest Level of Certainty)	A case will be classified as having "insufficient evidence" if a physician's diagnosis of ADEM is made, but evidence is insufficient to classify the patient at any higher level of diagnostic certainty (i.e., the abstraction data for that case does not contradict any of the Level 3 criteria but is missing information for at least one of the Level 3 criteria).		
	Absence of identified alternative diagnosis for clinical findings.		
Level 5 (Not a case)	If a case does not meet the criteria necessary for classification as Brighton Level 1, 2, or 3, is not diagnosed as ADEM by a physician, or has a definitive alternate		
	diagnosis documented in the chart, the patient will be classified as "not ADEM."		

Abbreviations: ADEM: acute disseminated encephalomyelitis.

The adjudicator will record the date, or estimated date, that symptoms first appeared per information in the chart. This will be the date used in the final analyses, described in Section 7.7. The onset date is crucial to determining whether the outcome occurred during the risk or control window.

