2. SYNOPSIS

Title

A post-marketing active surveillance study to evaluate the risk of Guillain-Barré syndrome, acute disseminated encephalomyelitis, and atrial fibrillation in adults 50 years and older vaccinated with GSK's *Arexvy* vaccine in the United States.

Rationale and background

Across GlaxoSmithKline Biologicals SA (GSK) respiratory syncytial virus (RSV) vaccine trials in adults 60 and older up to initial marketing authorization by Food and Drug Administration (FDA) in May 2023, inflammatory neurologic events were reported in 3 of 17 922 participants within 42 days after receipt of *Arexvy*. Reported events included 1 case of Guillain-Barré syndrome (GBS) and 2 cases of acute disseminated encephalomyelitis (ADEM), though the reporting investigator later revised the 2 ADEM diagnoses as hypoglycemia and dementia for 1 event and a cerebrovascular event for the other.

In addition, in the pivotal efficacy Phase 3 trial, a higher number of participants in the intervention group reported atrial fibrillation (AF) within 30 days after injection than the control group. This imbalance was no longer observed within 6 months after vaccination. After administration of a second dose of *Arexvy* in participants from this Phase 3 trial, an imbalance in AF events was observed within 6 months after vaccination, but not within 30 days after vaccination. In a Phase 3 trial evaluating the safety and the non-inferiority of the immune response of *Arexvy* in adults 50-59 years of age compared to adults ≥ 60 years of age, 1 AF event was reported among the 769 adults 50-59 years of age and 4 events were reported among the 381 adults ≥ 60 years of age.

Arexvy was approved for use in adults 60 years of age and older in May 2023, and the approval extended to individuals 50 through 59 years of age who are at increased risk for lower respiratory tract disease (LRTD) caused by RSV in June 2024. This study will include adults \geq 50 years of age.

Research question and objectives

The study will evaluate whether *Arexvy*, a recombinant adjuvanted RSV vaccine RSVPreF3 OA, is associated with an increased risk of new-onset GBS, new-onset ADEM, and new-onset AF within specified time periods after vaccination among people \geq 50 years of age.

The primary objectives are to assess the risk of: 1) new-onset GBS, and 2) new-onset ADEM, identified within 42 days after *Arexvy* vaccination and confirmed by clinician review of hospital records.

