7.5. Study size

The sample size and power calculations are estimated for the primary outcomes of the study, GBS and ADEM, and the primary risk (days 1-42) and control (days 43-84) windows. In the US, background rates of GBS reported in the literature range from 1.6 to 6.3 per 100 000 person-years in the overall population. In those ≥ 60 years of age, the IRs vary from 2.4 to 4.7 per 100 000 person-years in studies conducted over several years between 1935 and 1987 [Law, 2021]. More recent publications are reporting IR ≥ 4 GBS cases per 100.000 person-years in older adults. A study conducted in the US on background rates of adverse events of special interest reported a GBS IR of 4.6 per 100.000 person-years in adults ≥ 65 years of age [Moll, 2023]. The background rate in the analysis conducted by [Lloyd, 2024] was 4.4 per 100,000 person-years (unpublished). Background rates of ADEM range from 0.3 to 0.6 per 100 000 person-years in the overall population [Pohl, 2016].

The estimated number of vaccinated individuals needed to detect an association between *Arexvy* and the outcomes, assuming 80% statistical power, a two-sided alpha = 0.05, and an equal duration of 42 days for the risk window and 42 days for the control window, are

reported in Table 8 for GBS and ADEM for a range of RRs to be detected and a range of IR for the outcomes. Table 9 is for AF and is based on risk and control windows of 8 days.

Using a background rate for GBS of 4.5 cases per 100 000 person-years (taken as the average from [Lloyd, 2024] (4.4) and Moll, 2023 (4.6)), a total number of 69 cases in the combined risk and control intervals provides 80% power to reject the null hypothesis of no association when the true RR is \geq 2.0. Approximately 4.4 million vaccinated patients are needed to accrue the number of cases of GBS (Table 8).

Using a background rate for ADEM cases of 0.45 per 100 000 person-years, a total number of 12 cases in the combined risk and control intervals provides 80% power to reject the null hypothesis of no association when the true RR is \geq 7.0. Approximately 3.9 million vaccinated patients are needed to accrue the number of cases of ADEM (Table 8).

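### Table 6 requires that no alternative diagnosis be identified for possible ADEM (Level 4) but not for confirmed ADEM (Levels 1-3), unlike the GBS table it is meant to follow

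*Protocol*

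**What the plan says.** Section 7.3.2.3 of the protocol opens by saying that ADEM ascertainment and confirmation follow the GBS approach. On which tiers count it says: "ADEM cases identified as Brighton Level 1, 2, or 3 will be considered medical record-confirmed cases". Section 7.7.2.3 restricts the primary ADEM analysis to confirmed cases; Level 4 (possible) cases enter only in a sensitivity analysis.

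Table 6 defines the levels. At Level 3 the sole criterion is "Focal or multifocal findings referable to the central nervous system, including one or more of the following", followed by a list that includes encephalopathy, motor weakness and altered reflexes. MRI and course conditions belong to Levels 1 and 2. At Level 4 the table adds "Absence of identified alternative diagnosis for clinical findings". That line does not appear at Levels 1, 2 or 3.

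Table 5, for GBS (section 7.3.2.2), carries "Absence of identified alternative diagnosis for weakness" at each of Levels 1, 2, 3 and 4.

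Level 5 of Table 6 classifies a patient as not ADEM on any of three grounds: the criteria for Levels 1-3 are not met, no physician diagnosed ADEM, or the chart documents a definitive alternate diagnosis.

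On size, section 7.5 states: "Using a background rate for ADEM cases of 0.45 per 100 000 person-years, a total number of 12 cases" in the two windows combined gives 80% power at a true RR of 7 or more.

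**The concern.** An ordered scale of diagnostic certainty should not ask more of its lower tier than of its higher one. On alternative diagnoses Table 6 does. A patient with an identified but not definitive alternative explanation cannot be possible ADEM, yet nothing in the rows for Levels 1-3 stops the same patient from being confirmed. This matters most at Level 3, where a single CNS finding suffices and many other illnesses could produce it.

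Chart review is where specificity is meant to come from. Section 7.3.2.3 says that case finding deliberately favours sensitivity because charts will be sought for every event, and Table 4 lists no published ICD-10-CM algorithm for ADEM. The sensitivity analyses in section 7.7.2.3 that change diagnostic certainty only widen the case set, by adding possible cases or events with unobtainable charts. None named there narrows it to Levels 1-2.

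At stake is a primary safety outcome resting on 12 cases. Events unrelated to vaccination would be expected to fall evenly across two equal windows and move the IRR toward 1, that is, toward missing a harm. They would also count toward the case total that triggers the final analysis (section 7.7).

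**Working it through.** **Step 1. The two tables side by side**

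| Level | Status | GBS (Table 5): absence of an identified alternative required? | ADEM (Table 6): absence of an identified alternative required? |
|---|---|---|---|
| 1 | confirmed | yes | no |
| 2 | confirmed | yes | no |
| 3 | confirmed | yes | no |
| 4 | possible | yes | yes |
| 5 | not a case | definitive alternate, or no physician diagnosis | definitive alternate, or no physician diagnosis |

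Level 5 is worded alike in both tables, so it does not explain why the line is missing from the ADEM rows.

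**Step 2. What Level 5 leaves open.** Take a patient with an ADEM code, a physician's ADEM diagnosis and one listed CNS finding:
- Definitive alternate diagnosis in the chart: the patient fits both Level 3 and Level 5, and the table does not say which prevails.
- Alternative identified but not definitive: Level 5's alternate-diagnosis ground does not apply, Level 4 is barred, and Level 3 is met. The patient is confirmed.
- Normal MRI or documented relapse, without histopathology: Levels 1 and 2 are not met, but Level 3 is. The patient is confirmed.

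**Step 3. Reproduce the planned case number.** Section 7.5 gives the inputs: "assuming 80% statistical power, a two-sided alpha = 0.05", RR 7, and equal 42-day windows, so r = 0.5. The signed-root likelihood-ratio formula for self-controlled case series, the method cited under Table 8, is

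n = (z_a + z_b √B)² / A, with b = ln RR, p = RR·r/(RR·r + 1 − r), A = 2[p·b − ln(RR·r + 1 − r)], B = (b²/A)·p(1 − p).

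Here b = 1.946, p = 7/8, A = 0.633 and B = 0.655, so n = (1.960 + 0.842 × √0.655)² / 0.633 = 11.02, rounded up to 12. This matches the protocol. The vaccinee figure also reproduces: 2 control-window cases / (0.45 × 10⁻⁵ × 42/365.25) = 3.865 million.

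**Step 4. Exact power at 12 cases.** Under no association each case falls in the risk window with probability 0.5. P(X ≥ 10) = 0.019 and P(X ≥ 9) = 0.073, so a two-sided 0.05 test declares an excess only at 10 or more of 12. At p = 7/8 the power is 0.818.

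**Step 5. Illustrative dilution.** Let a share f of the 12 counted cases be non-ADEM with RR 1. Then p_obs = (1 − f)·7/8 + f·0.5 and the expected IRR = p_obs/(1 − p_obs).

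| f (assumed) | p_obs | Expected IRR | Exact power, 12 cases |
|---|---|---|---|
| 0 | 0.875 | 7.0 | 0.818 |
| 0.10 | 0.8375 | 5.2 | 0.692 |
| 0.25 | 0.781 | 3.6 | 0.493 |
| 0.33 | 0.751 | 3.0 | 0.395 |

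The documents give neither f nor the share of cases expected at Level 3. The table shows sensitivity to f and does not predict it.

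**The case against.** The strongest reply is that the Level 3 row should not be read alone. A reader might infer that Table 6 has no exclusion of other diagnoses and that one non-specific sign is enough to confirm ADEM. The documents do not support that. A retained Level 3 patient has an ADEM code, a physician's ADEM diagnosis, CNS findings, no definitive alternate diagnosis if Level 5 is applied, and adjudication by two clinicians blinded to vaccination date, with a third to settle disagreement. This stands, and it narrows the gap to identified but non-definitive alternatives, the unstated precedence of Level 5, and the normal-MRI or relapse cases. It does not close the gap, because the adjudicators still apply Table 6.

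A reader might also take the two trial reports as proof that Level 3 admits false cases, since "the reporting investigator later revised the 2 ADEM diagnoses as hypoglycemia and dementia for 1 event and a cerebrovascular event for the other". They show that an initial ADEM label can be wrong. Once such a diagnosis is definitive in the chart, however, Level 5 addresses it.

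Third, Table 6 is presented as a named external case definition whose source is not at hand, so its fidelity to that source cannot be checked here. Rewriting Level 3 to require that MRI was unavailable and no relapse occurred would be a debatable departure from it. That stands, and is why a restricted sensitivity analysis is the better way to cover those patients.

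Fourth, the power comparison assumes each false case is replaced by a true one. If the 30 June 2030 end date binds instead, exclusion leaves fewer cases. With 1, 2, 3 or 4 of 12 false, keeping them gives exact power of 72%, 61%, 48% or 37%, and dropping them gives 59%, 64%, 69% or 34%. The gain in power is therefore not uniform. The reduction in bias does not depend on it.

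Finally, section 7.9 acknowledges outcome misclassification and says quantitative bias analysis may be done. That is optional and does not repair the case definition.

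**Conclusion.** The point holds in a limited form and should be fixed. As written, an identified but non-definitive alternative diagnosis disqualifies a patient from possible ADEM and not from confirmed ADEM. This departs from Table 5 and from the stated intention to treat ADEM like GBS. The table also leaves open which level applies when Level 5 and a confirmed level both fit.

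The direction of bias, toward 1, rests on one assumption: that the wrongly confirmed events are unrelated to vaccination. The size is not known. The illustrated fall in exact power from 82% to between 69% and about 40%, with an expected IRR of 5.2 to 3.0 instead of 7, rests on an assumed false share of 10% to 33% among 12 cases. It should not be read as an estimate of what will happen. The planned 12 cases at RR 7 are correctly calculated for true ADEM cases. Table 6 breaks across pages in the text reviewed, so its layout should be confirmed against the source file.

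**What to change.** 1. Add to Table 6, at Levels 1, 2 and 3, the alternative-diagnosis line now given only at Level 4, as Table 5 does for GBS.
2. State that Level 5 takes precedence over Levels 1-3 where no physician diagnosed ADEM or a definitive alternate diagnosis is documented. Tie the precedence to these two grounds: the remaining ground, not meeting Levels 1-3, would literally sweep up every Level 4 case as well.
3. Add to section 7.7.2.3 a sensitivity analysis of the primary ADEM comparison restricted to Levels 1-2. It also shows the influence of Level 3 cases with a normal MRI or a relapse, without altering Level 3 itself.

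The cost is an edit to one table, a matching edit to the adjudication form, and one further analysis of data already collected. No extra charts or readers are needed, and the stated case numbers do not change. The downside is slightly fewer confirmed events, and so possibly slower accrual. Charts are adjudicated after each annual query, so a late change would mean re-adjudicating earlier cases.
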